4.2.2.7 Death Associated with COVID-19

Death associated with COVID-19 is defined as death in a participant with COVID-19 who died within 28 days of the first positive specimen date OR died more than 28 days after the first specimen date and COVID-19 is mentioned as an immediate or underlying cause of death on the death certificate. This endpoint will be analyzed as data collected in CRF.

4.2.2.8 Pregnancy

This information will be listed as collected. No derivation or imputation will be done.

4.2.2.9 Action Taken

Solicited injection site/systemic reactions after any vaccine injection(s) will be summarized, by action taken. Main analysis will be applied for this endpoint. Complementary analysis may be applied.

4.2.2.10 Seriousness

This information will be summarized as collected. No derivation or imputation will be done. Main analysis will be applied for this endpoint. Complementary analysis may be applied.

4.2.2.11 Outcome

This information will be summarized as collected. No derivation or imputation will be done. Main analysis will be applied for this endpoint. Complementary analysis may be applied.

4.2.2.12 Causal Relationship

This information will be summarized as collected. Missing causality (relationship) will be handled as described in [Section 3.4.7.1.2](#). Main analysis will be applied for this endpoint. Complementary analysis may be applied.

4.2.2.13 Adverse Events Leading to Study Discontinuation

A flag will be available in the clinical database for all AEs in order to identify AEs leading to discontinuation. This information will be analyzed as collected.

In general, the items that are counted are:

- For subject disposition: if subject did not complete the study due to AE as recorded in Completion at End of Study form
- For safety overview: if subject did not complete the study due to AE as recorded in Completion at End of Study form or had any solicited or unsolicited AEs causing study discontinuation / termination as recorded in solicited reaction or unsolicited AE forms within the time period indicated
- For summary of unsolicited AEs by system organ class (SOC) / PT: A solicited AE that has “Caused Study Termination” checked that is at least Grade 1 or an unsolicited AE that has “Caused Study Termination” checked that is at least Grade 1 or missing and is within the time period indicated

Main analysis and complementary analysis will be applied for this endpoint.

4.2.3 Immunogenicity

4.2.3.1 Computed Values for Analysis

In order to appropriately manage extreme values (< lower limit of quantification [LLOQ]) for analysis purposes, the following computational rule is applied to the values provided in the clinical database for each blood sample (BL) drawn:

- If a value is < LLOQ, then use the computed value LLOQ/2.
- If a value is between LLOQ and ULOQ, then use the value reported.
- If a value is > ULOQ, then use ULOQ.
- Immunogenicity values at baseline (D01) with values < LLOQ are considered as negative whereas values \geq LLOQ are considered as positive.

For SARS-CoV-2 pseudovirus neutralization assay at Monogram, LLOQ is < 40 and ULOQ is \geq 787339.

For SARS-CoV-2 spike protein antibody serum IgG ELISA (Nexelis), LLOQ is 18.9.

4.2.3.2 Fold-rise

The derived endpoint fold-rise is driven by both baseline and post-vaccination computed values as described in [Section 4.2.3.1](#) and is computed as individual titer ratio:

- Post-vaccination value divided by baseline value.

Note: If baseline or post-baseline is missing, then fold-rise is missing.

4.2.3.3 Responders

The responder's endpoint is determined by both baseline and post-baseline computed values with quantifiable titer values. Participants are identified as responders based on any one of the criteria:

- Baseline computed values < LLOQ and post-baseline values \geq LLOQ at each pre-defined time point
- Baseline computed values \geq LLOQ and < ULOQ with a 4-fold increase in post-baseline titers at each pre-defined timepoint
- Baseline value \geq ULOQ is not within the scope of the responder's definition (not applicable) and will be out of the analysis

Note: If baseline or post-baseline is missing, then responder endpoint for the corresponding timepoint(s) is missing.

4.2.3.4 Cellular Immune Response

Measurements of B cell responses and T cell responses will be tested independently, and data will be analyzed as reported by GCI.

4.2.3.5 Mucosal Immune response

Mucosal Ig values are derived by testing samples in duplicate in an indirect ELISA and comparing the Optical Density to a Cutoff Calibrator included with the kit. The cutoff value (Cutoff OD) is the mean value of the optical densities of the Cutoff Calibrator. Specimen results are calculated using the S / CO ratio: Specimen ratio = Specimen OD / Cutoff OD.

A specimen ratio less than or equal to 0.8 is negative for the presence of anti-SARS-CoV-2 antibodies, between 0.8 and 1.0 is equivocal for the presence of anti-SARS-CoV-2 antibodies, and greater than 1.0 is considered to be positive for the presence of anti-SARS-CoV-2 antibodies.

As samples are tested in duplicate, if one or more results are positive the final interpretation of the specimen is positive; if the repeat results are equivocal or negative the final interpretation is equivocal, and if both results are negative the final interpretation of the specimen is negative.

4.2.4 Derived Other Variables

4.2.4.1 Age for Demographics

The age of a participant in the study will be the calendar age in years at the time of inclusion and will be analyzed as collected in CRF.

Age group

The calendar age will be used for demographics summary and age-group definition. The age group of a participant in the study will be based on the calendar age as follows:

- “18 to 55 years”: from the day of the 18th birthday to the day before the 56th birthday
- “ ≥ 56 years”: from the day of the 56th birthday onwards, with no upper age limit

4.2.4.2 High-Risk Medical Conditions

The high-risk medical conditions at baseline are analyzed as collected in the CRF pages of high-risk medical conditions, smoking and BMI calculation.

Definition of High-Risk Medical Conditions

Comorbidities associated with increased risk of severe COVID-19 are defined as: High-risk conditions considered to be associated with an increased risk of severe COVID-19 (<https://www.cdc.gov/coronavirus/2019-ncov/need-extra-precautions/evidence-table.html>) and include: cancer; chronic kidney disease; chronic obstructive pulmonary disease (COPD); immunocompromised state from solid organ transplant; immunocompromised state from other causes (blood or bone marrow transplant, immune deficiencies, HIV, use of corticosteroids, or use of immunosuppressors); obesity (body mass index of 30 kg/m^2 or higher); heart conditions such as heart failure; coronary artery disease or cardiomyopathies; sickle cell disease; thalassemia; type 1 or type 2 diabetes mellitus; moderate-to-severe asthma; cerebrovascular disease; cystic fibrosis; hypertension/high blood pressure; neurologic conditions; hepatic disease; pulmonary fibrosis; smoking.

High-Risk Medical Conditions Group

- Yes: at least one high-risk medical conditions as defined above. Participants who are current smokers with either tobacco use or electronic cigarette use will be considered as in high-risk medical conditions group.
- No: no high-risk medical conditions as defined above. Participants who never smoked or are former smokers (either tobacco use or electronic cigarette use) will be considered as not in high-risk medical conditions group.

4.2.4.3 Duration of a Subject in the Trial

The duration of a subject participation in the study is computed as follows:

- Maximum (Visit dates, Termination date, Death date) – V01 date + 1.

For ongoing subject in the interim analysis, the duration of a subject participation in the study is computed as follows:

- Minimum (Database lock/Database extraction date, Termination date, Death date) – V01 date + 1.

4.2.4.4 Duration of the Study

The duration of the study is computed in days as follows:

- Maximum (latest date of Visit or contact, latest date of termination) – minimum (date of V01) + 1

For interim analysis, the duration of the study is computed in days as follows:

- Maximum (Database lock/Database extraction date, Termination date, Death date) – minimum (date of V01) + 1.

4.2.4.5 Prior On-study Booster Injection

The duration in month of the prior on-study booster injection for Supplemental Cohort Booster Groups participants is computed as follows:

- (date of booster injection – date of last prior COVID-19 injection) / 30.44

4.2.4.6 Safety Follow-up Duration

The safety follow-up duration is computed as follows:

- Received other COVID-19 vaccination: first date of other COVID-19 vaccination - V01 date
- Not received other COVID-19 vaccination: Maximum (Database lock/Database extraction date, Termination date, Death date) – V01 date

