All Supplemental Cohort participants will be followed for the duration of the study to capture occurrences of COVID-19 through passive surveillance wherein participants will be instructed to contact the site if they experience symptoms/conditions of a COVID-19-like illness at any time during the study. In addition, active surveillance will be undertaken in all participants wherein all participants will be contacted once every 2 weeks starting after the last injection to enquire about development of COVID-19-like illness.

The duration of participation in the study for each participant will be:

- Supplemental Cohorts 1 and 2: approximately 365 days post-booster injection (ie, approximately 366 days total)
- Supplemental Cohorts Comparator Groups: approximately 365 days post-injection 2 (ie, approximately 386 days total)

2 Objectives and Endpoints

Table 2.1: Objectives and endpoints

Primary Safety	
To assess the safety profile of all participants in each age group and in each study Intervention Group.	
 • Presence of unsolicited systemic AEs reported in the 30 minutes after each vaccination • Presence of solicited (pre-listed in the participant's diary card [DC] and [electronic] Case Report Form [CRF]) injection site reactions and systemic reactions occurring up to 7 days after each vaccination • Presence of unsolicited AEs reported up to 21 days after the last vaccination • Presence of serious adverse events (SAEs) throughout the study • Presence of AESIs throughout the study • Presence of MAAEs throughout the study
Primary Immunogenicity-Supplemental Cohort 1	

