4.2.1.1.5 Number of Days of Occurrence During the Solicited Period

Number of days of occurrence over the period considered is derived from the daily intensities computed as described in [Section 4.2.1.1.1](#). It corresponds to the number of days with daily

intensities of Grade 1, Grade 2, or Grade 3. Number of days of occurrence on the solicited period with a specified intensity may also be derived.

Main analysis, sensitivity analysis and complementary analysis will be applied by number of days of occurrence. The endpoint is derived from the general method mentioned above for sensitivity analysis and complementary analysis. Suppose participants receiving a non-study authorized/approved COVID-19 vaccine on Day X within the solicited collection period:

- The number of days of occurrence for main analysis will be derived on daily intensities from D01 to Day X-1.
- The number of days of occurrence for sensitivity analysis and complementary analysis will be derived from daily intensities collected over the entire solicited collection period.

Number of Days of Occurrence during the solicited period will be categorized into and displayed as 1-3 days, 4-7 days, and 8 days.

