4.2.1.1.7 Ongoing

Ongoing is derived from the last daily intensity of the solicited period computed as described in [Section 4.2.1.1.1](#) and the maximum intensity in the ongoing period. The Investigator’s ongoing flag is not used because the measurement would determine the ongoing status of the reaction.

- Ongoing: if the last daily intensity of the solicited period is at least Grade 1 and the maximum intensity on the ongoing period is at least Grade 1
- Not ongoing: if the last daily intensity of the solicited period is None or the maximum intensity on the ongoing period is None
- Missing: all other conditions (in this case, it is not included in the denominator of the ongoing analysis in the safety tables)

Ongoing status will be derived for main analysis, sensitivity analysis and complementary analysis. Ongoing status is derived from the general method mentioned above for sensitivity analysis and complementary analysis. Ongoing status for main analysis is derived as follows:

- If ongoing status for sensitivity analysis is ongoing or missing, the ongoing status will be missing
- If ongoing status for sensitivity analysis is not ongoing, the ongoing status will be analyzed as not ongoing

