A Pooled Primary Series Cohort as Supplemental Cohorts 2 Comparator Group was added in Protocol Amendment 4, version 8. The purpose is to maintain sufficient power for Cohort 2 hypothesis testing in primary analysis in case of a substantial shortfall in numbers of Comparator Group evaluable participants as the number of authorized and/or approved COVID-19 vaccines increases and RDT at baseline sensitivity to identify the Naïve participants is low. The pooling of evaluable participants from other trials of the same vaccine program is defined in SAP and the exploratory sensitivity analysis is added.

- Complementary assessment of external samples/data**

To further study immunogenicity profile of study vaccine, external samples/data will be analyzed along with study data. The assessment of external samples/data is considered as complementary analysis and corresponding part is added in SAP Section 4.3.

- Study design updated to remove Variant Prime Cohort 3**

The operational feasibility of recruiting SARS-CoV-2 naïve, unvaccinated participants has become significantly more challenging, data are not required for regulatory purposes.

- Enlarge the variant testing scope of Cohort 1 and Cohort 2 (Protein Primed Group)**

A randomized subset of 70 participants in Cohort 1 was originally planned to be tested for additional SARS-CoV-2 variants of concern including Delta. However, to address CBER requests, the Sponsor decided to expand the scope of testing and to perform the immunogenicity assessment for Delta in the whole Cohort 1 and Cohort 2 (Protein Primed Group) instead of only in a subset of participants. Thus, the VTAS will not be applicable to Cohort 1 variant testing results. The PPAS and FAS will be utilized for analyzing the variant testing results.

- Modify variant testing subset analysis set definition**

The Variant Testing Subset Analysis Set (VTAS) will have the blood sample time window adherence considered in order to know the per-protocol participants immunogenicity response. The Variant Testing Subset without consider the exclusion criteria will be utilized to see the immunogenicity results furthermore.

- Add study duration and safety follow-up duration calculation method for ongoing participants in interim analysis**

The database lock or data extraction date will be utilized for calculation on study duration and safety follow-up duration in ongoing participants under interim analysis scope.

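### Two separate derivation rules in SAP Section 4.2 are wrong as written: without another COVID-19 vaccine, safety follow-up always runs to database lock, and the main-analysis count of ongoing solicited reactions is always zero

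*SAP*

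**What the plan says.** **Follow-up duration.** SAP Section 4.2.4.6 has two branches. Recipients of another vaccine are cut at that date: "Received other COVID-19 vaccination: first date of other COVID-19 vaccination - V01 date". Everyone else falls under "Not received other COVID-19 vaccination: Maximum (Database lock/Database extraction date, Termination date, Death date"), less the V01 date. Neither branch distinguishes interim from final analysis, or ongoing participants from those who have left.

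Three other places in the SAP bear on this:
- Section 4.2.4.3 (participant-level duration) uses "Minimum (Database lock/Database extraction date, Termination date, Death date") for ongoing subjects at interim. Its general rule takes the latest of visit, termination and death dates and contains no lock date.
- Section 4.2.4.4 uses "Maximum (Database lock/Database extraction date, Termination date, Death date") at interim, but for the duration of the whole study, counted from the earliest V01.
- Section 5 explains that the lock or extraction date was introduced to calculate "study duration and safety follow-up duration in ongoing participants under interim analysis scope".

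**Ongoing status.** Section 4.2.1.1.7 gives a general derivation (*ongoing*, *not ongoing* or *missing*), which the sensitivity and complementary analyses use. It leaves *missing* out of the denominator. For the main analysis it says "If ongoing status for sensitivity analysis is ongoing or missing, the ongoing status will be missing", while *not ongoing* stays as it is. The neighbouring Sections 4.2.1.1.2, 4.2.1.1.5 and 4.2.1.1.6 all confine their special main-analysis handling to participants who receive a non-study "vaccine on Day X within the solicited collection period". Section 4.2.1.1.7 has no such condition.

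**The concern.** In 4.2.4.6 the termination and death terms can never act. A participant who died in week three is given the same follow-up as one still attending visits, and at a final lock every completer gains time after the last visit. The published follow-up summary would overstate how long participants were observed. The excess grows with early exit and with the gap between last visit and lock.

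In 4.2.1.1.7, a rule that makes sense only for participants whose data are censored at a non-study vaccination is written as applying to everyone. Programmed literally, the main safety output would show no reaction ongoing beyond the solicited period in any group, whatever was reported. Safety is a primary objective, so a main output fixed in advance at zero deserves correction. The two slips have different causes and need separate corrections.

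**Working it through.** The SAP states no figure for either quantity, so there is nothing to reproduce. The check applies each rule literally to example cases. Lock days, exit days and reaction counts are assumptions. The 3% and 10% are borrowed from the attrition assumptions in Section 3.2.1, which concern loss by D15 and D36 rather than early exit over a year. They serve here only as illustrative shares.

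**1. Follow-up, no other COVID-19 vaccine**

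Let L, T and D be the days from V01 to lock, termination and death. Any recorded T or D satisfies T ≤ L and D ≤ L, so max(L, T, D) = L always.

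| Participant | Lock day | Rule as written | Minimum |
|---|---|---|---|
| Died day 20 | 120 | 120 | 20 |
| Withdrew day 30 | 120 | 120 | 30 |
| Still ongoing | 120 | 120 | 120 |
| Died day 200 | 450 | 450 | 200 |
| Completed day 365 | 450 | 450 | 365 |

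The two rules agree only for participants still ongoing, the group named in Section 5.

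Group means, with a share f leaving uniformly over the period:

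- Lock at day 450, completion at day 365. This follows the booster arms in Section 1: "Supplemental Cohorts 1 and 2: approximately 365 days post-booster injection (ie, approximately 366 days total"). True mean = f × 182.5 + (1 − f) × 365; rule as written = 450.
  - f = 3%: 5.475 + 354.05 = 359.5, so 450/359.5 = 1.25 (+25%).
  - f = 10%: 18.25 + 328.5 = 346.75, so 450/346.75 = 1.30 (+30%).
- Lock at day 120, no one yet complete. True mean = f × 60 + (1 − f) × 120; rule as written = 120.
  - f = 3%: 1.8 + 116.4 = 118.2 (+1.5%).
  - f = 10%: 6 + 108 = 114 (+5.3%).

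Most of the day-450 excess comes from completers, not dropout: with f = 0 it is already 450/365 = 1.23 (+23%).

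**2. Ongoing status, main analysis**

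Mapping as written: *ongoing* → *missing*; *missing* → *missing*; *not ongoing* → *not ongoing*. No input maps to *ongoing*, so the numerator is zero by construction.

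| General derivation (ongoing / not ongoing / missing) | Sensitivity | Main as written |
|---|---|---|
| 20 / 180 / 5 | 20/200 (10%) | 0/180 |
| 60 / 140 / 5 | 60/200 (30%) | 0/140 |
| 200 / 0 / 5 | 200/200 (100%) | 0/0, undefined |

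If the rule is limited to recipients of a non-study vaccine within the solicited period, and none of these participants received one, 20/200 stays 20/200.

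**The case against.** The best defence is that the intent can be recovered. Section 5 ties the lock date to ongoing participants at interim, where Maximum and Minimum coincide, and the general rule in 4.2.4.3 already gives correct time in study for those who left. Likewise, Section 4.2.1 explains that main and sensitivity analyses differ because main data are censored at a non-study vaccine, which suggests whom 4.2.1.1.7 meant. That shows the intention but does not alter the stated rules. Section 4.2.4.6 is the only rule for safety follow-up and has no ongoing-at-interim limit, and 4.2.1.1.7 lacks the condition that its neighbours spell out.

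A second defence is the note to Figure 1.1: participants who discontinue early are still contacted about SAEs and AESIs. So the withdrawal date may not be the true end of observation for a withdrawn participant. This stands as a caution on the withdrawal examples. It cannot justify follow-up to lock for a death, or for a completer whose planned participation has ended.

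Third, the sensitivity table would show the unaltered ongoing status. Under Section 4.2.1, however, that analysis is generally run only if at least 15 subjects have different values, so with fewer ongoing reactions it may not be produced.

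Three stronger readings are tempting and are not supported:
- That everyone who leaves early is affected. Recipients of another COVID-19 vaccine are already cut at that date, and Section 4.2.1 expects such vaccination to be frequent in the Comparator Group.
- That adverse event rates are diluted. Section 3.4.3 reports percentages of participants with Clopper-Pearson intervals and no person-time rate.
- That ongoing reactions vanish from the main analysis. Presence, maximum intensity and number of days of occurrence still count them; only the ongoing-status output is wrong.

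**Conclusion.** Both rules give wrong results as written, and each should be corrected before database lock.

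The follow-up error is confined to participants without another COVID-19 vaccine and to a descriptive summary. Its size depends on when the lock falls: about 1.5% to 5% at day 120 and 25% to 30% at day 450, given uniform exits, 3% to 10% early exit and, for the later lock, completion at day 365. The SAP fixes no lock day, so these are illustrations, not predictions.

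The ongoing-status error needs no assumption about the data: the main-analysis count is zero for any input. It is limited to that one output.

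Neither error touches an immunogenicity hypothesis or an adverse event percentage, so the point does not call the trial's conclusions into question.

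**What to change.** **Section 4.2.4.6.**
- In the branch for participants with no other COVID-19 vaccine, replace Maximum with Minimum of the lock/extraction, termination and death dates. State that the end date for completers is the last visit or contact.
- Say whether a later safety call to a withdrawn participant extends follow-up.
- Leave the branch for recipients of another vaccine as vaccination date minus V01, with no added day. For vaccination on Day X this gives X − 1 days, which matches the D01 to Day X − 1 window in 4.2.1.1.2. Adding 1, as 4.2.4.3 does, would count a day that the main analysis excludes.

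**Section 4.2.1.1.7.** Apply the set-to-missing rule only to participants who received a non-study COVID-19 vaccine on Day X within the solicited collection period, as in 4.2.1.1.2, 4.2.1.1.5 and 4.2.1.1.6. For everyone else, use the general derivation in the main analysis.

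The cost is a few sentences of SAP text and the matching derivation code. Reported follow-up will be shorter wherever participants died, withdrew or completed before lock. Sample size and alpha are unaffected.
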